## 1. INTRODUCTION

The objective of this Integrated Statistical Analysis Plan (iSAP) is to describe the analysis of Integrated Summary of Safety (ISS) that will be performed on all relevant safety data to support second-line tarlatamab filing.

Studies under the scope of ISS are:

- Monotherapy cohorts of 20160323 (Parts A, D, E, F and G) :  
A Phase 1 Study Evaluating the Safety, Tolerability, and Pharmacokinetics of Tarlatamab in Participants With Small Cell Lung Cancer.
- 20200491 (Parts 1, 2, 3):  
A Phase 2 Study Evaluating the Efficacy, Safety, Tolerability, and Pharmacokinetics of Tarlatamab in Participants with Relapsed/Refractory Small Cell Lung Cancer After Two or More Prior Lines of Treatment.
- Tarlatamab arm of 20210004:  
A Randomized, Open-label, Phase 3 Study of Tarlatamab Compared With Standard of Care in Participants With Relapsed Small Cell Lung Cancer After Platinum-based First-line Chemotherapy.

Safety data from study 20200491, monotherapy cohorts of study 20160323 and tarlatamab arm of study 20210004 will be integrated and analyzed. **If needed, additional studies may be added after data are available.**

Output headers are shown below:

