#### **5.4.4 Adverse Events**

##### **5.4.4.1 All Adverse Events**

The MedDRA version **27.0** or later will be used to code all events categorized as adverse events to a system organ class and a preferred term. The severity of each adverse event will be graded using CTCAE version 5.0 for study 20200491 and tarlatamab arm of study 20210004. The severity of each adverse event for monotherapy cohorts of study 20160323 will be converted from CTCAE version 4.0 to 5.0 where possible. CRS and ICANS events from study 20200491 and tarlatamab arm of study 20210004 are graded according to ASTCT 2019. CRS and ICANS events from monotherapy cohorts of study 20160323 will be converted from Lee et al. 2014 to ASTCT 2019 where possible.

The participant incidence of adverse events will be summarized for all TEAEs, treatment-related TEAEs, serious TEAEs, grade 3 or higher TEAEs, fatal TEAEs, TEAEs leading to dose interruption and/or reduction of tarlatamab and TEAEs leading to discontinuation of tarlatamab.

Worst grade is derived as the maximum grade (per the applicable grading scale CTCAE / ASTCT) for each preferred term per participant.

Detail on the derivation of worst grade at event level will be provided in the TFL shell document.

Participant incidence of all TEAEs and TRAEs will be summarized as outlined in the [Table 3](#). When applicable, rows are sorted by system organ class (alphabetically) and

preferred term within system organ class (in descending order of frequency).

Overall summary of exposure-adjusted event rate of all TEAEs, serious TEAEs, grade 3 or higher TEAEs, fatal TEAEs, TEAEs leading to dose interruption and/or reduction of tarlatamab and TEAEs leading to discontinuation of tarlatamab will be produced. A separate overall summary of exposure-adjusted event rate of serious TEAEs will be provided.

Listing of TEAEs, listing of deaths during the studies will be produced with all the relevant fields.

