#### 5.4.4.2 Event of Interest (EOI)

EOIs identified for tarlatamab:

Cytokine Release Syndrome (AMQ Broad), Cytokine Release Syndrome (AMQ Narrow), Neutropenia (AMQ Broad), Neutropenia (AMQ Narrow), Immune effector Cell Associated Neurotoxicity Syndrome (ICANS) and associated neurological events (AMQ Broad), Neurological Events [Nervous system disorders (SOC) / Psychiatric disorders (SOC)], Hypersensitivity **broad** events [Hypersensitivity (SMQ Broad) / Anaphylactic reactions (SMQ Narrow)], **Hypersensitivity narrow events [Hypersensitivity (SMQ Narrow) / Anaphylactic reactions (SMQ Narrow)]**.

For the list of EOIs mentioned above, the participant incidence of treatment-emergent adverse events of interest (Amgen MedDRA Queries), grade  $\geq 2$ , grade  $\geq 3$ , grade  $\geq 4$ , serious, fatal, events leading to dose interruption and/or reduction of tarlatamab and events leading to discontinuation of tarlatamab will be summarized.

Summary of all treatment-emergent EOIs, treatment-emergent serious EOIs, grade 3 or higher treatment-emergent EOIs, treatment-emergent fatal EOIs, treatment-emergent EOIs leading to dose interruption and/or reduction of tarlatamab and treatment-emergent EOIs leading to discontinuation of tarlatamab by their categories and preferred term will be provided. Similar summaries will be repeated for treatment-related treatment-emergent adverse events of interest.

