Additionally, summaries of time to first onset of treatment-emergent EOIs from first tarlatamab administration (days), time to first onset of treatment-emergent EOIs after each dose from last prior tarlatamab administration (days), and duration of treatment-emergent EOIs (days) will be provided. Summaries of time to first onset of treatment-emergent EOIs from first tarlatamab administration (hours), and time to first onset of treatment-emergent EOIs after each dose from last prior tarlatamab administration (hours) will be provided for CRS (AMQ Narrow) only. Summaries of treatment-emergent CRS (AMQ Narrow) by dose, time from onset of grade 1 treatment-emergent CRS (AMQ Narrow) to grade 2 or higher treatment-emergent CRS (AMQ Narrow) by dose, time from onset of grade 1 treatment-emergent CRS (AMQ Narrow) to grade 2 treatment-emergent CRS (AMQ Narrow), duration of treatment-emergent CRS (AMQ Narrow) for participants that required tocilizumab, participant incidence of treatment-emergent CRS (AMQ Narrow) treated with tocilizumab, participant incidence of recurrent treatment-emergent CRS (AMQ Narrow), summary of treatment-emergent CRS (AMQ Narrow) rebound incidence in participants following recommended tarlatamab dosage for restarting therapy after dose delay, participant incidence of intervention utilization in relation to treatment-emergent CRS (AMQ Narrow), participant incidence of intervention utilization within and after 24 hours of last prior dose at cycle 1 day 1 and cycle 1 day 8 for grade 2 or higher treatment-emergent CRS (AMQ Narrow), participant incidence and time to onset for grade 2 or higher treatment-emergent CRS (AMQ Narrow) by dose will be presented, other analyses for CRS (AMQ Narrow) may be provided as well if needed. Participant incidence of treatment-emergent ICANS and associated neurological events by last prior tarlatamab administration, participant incidence of treatment-emergent ICANS and associated neurological events by last prior tarlatamab administration visit and worst grade, participant incidence of recurrent treatment-emergent ICANS and

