#### 5.5 Postmarketing Requirement

In order to meet the postmarketing requirement from FDA, analyses of adverse events for different periods, severity, and outcome of the known serious risks of CRS and ICANS will be further characterized based on the integrated safety analysis of data from participants with extensive stage SCLC. A comprehensive analysis will be included from all available data sources including but not limited to participant-level and pooled analyses of study 20200491 and monotherapy cohorts of study 20160323 and tarlatamab arm of study 20210004.

Summaries of all EOIs, serious EOIs, time to onset of EOIs from first tarlatamab administration (days), time to onset of serious EOIs from first tarlatamab administration (days), time to onset of EOIs from last prior tarlatamab administration (days), time to onset of serious EOIs from last prior tarlatamab administration (days), duration of EOIs (days) and duration of serious EOIs (days) will be provided by following periods:

- Period 1: From cycle 1 day 1 to 90 days after cycle 1 day 1 or end of treatment, whichever occurs earlier.
- Period 2: From 90 days after cycle 1 day 1 to end of treatment.
- Period 3: From end of treatment to end of safety follow up.
- Period 4: From end of safety follow up to end of long term follow up or end of study, whichever occurs later .

Similar summaries above will be repeated for pituitary dysfunction events by period 3 and period 4. Pituitary dysfunction events are identified by Global Safety Officer using preferred terms coded MedDRA version **27.0** or later.

Severity and outcome of the known serious risk of CRS, ICANS and neurologic toxicity are mentioned in [section 5.4.4.2](#).

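### The integrated SAP summarizes pituitary dysfunction as a group only after end of treatment, so on-treatment events get no pituitary-specific participant count, onset or duration summary

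*SAP*

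**What the plan says.** The SAP is an integrated safety plan covering three studies, including the tarlatamab arm of this trial: "Safety data from study 20200491, monotherapy cohorts of study 20160323 and tarlatamab arm of study 20210004 will be integrated and analyzed".

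Section 5.5 (Postmarketing Requirement) sets four periods. Periods 1 and 2 are on treatment, divided at 90 days after the first dose. Period 3 runs from end of treatment to the end of safety follow-up, and Period 4 covers the time after that. For events of interest, a series of summaries ending with "duration of EOIs (days) and duration of serious EOIs (days) will be provided by following periods" is planned for all four. For pituitary dysfunction the text is: "Similar summaries above will be repeated for pituitary dysfunction events by period 3 and period 4". The group is formed from a term list: "Pituitary dysfunction events are identified by Global Safety Officer using preferred terms coded MedDRA version".

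Section 5.4.4.2 gives the list headed "EOIs identified for tarlatamab": cytokine release syndrome, neutropenia, ICANS with associated neurological events, neurological events, and hypersensitivity. Pituitary dysfunction is not on it. The grouped analyses in that section are tied to the list: "For the list of EOIs mentioned above, the participant incidence of treatment-emergent adverse events of interest (Amgen MedDRA Queries"), and likewise "summaries of time to first onset of treatment-emergent EOIs from first tarlatamab administration (days") and the duration summaries.

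Section 5.4.4.1 and its Table 3 cover all treatment-emergent events, and "Listing of TEAEs, listing of deaths during the studies will be produced with all the relevant fields".

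**The concern.** Protocol section 2.3 names pituitary dysfunction as a possible safety concern of tarlatamab. Protocol Table 6-2 manages it during treatment: watch for signs, hold the next dose once it is confirmed, and restart when the participant is stable on hormone replacement. To judge that guidance, a reader needs to know how many participants developed it on treatment, when it began and how long it lasted. The SAP plans a grouping that would answer this, but applies it only after treatment has ended.

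A second consequence concerns timing. Summaries of onset from first dose, restricted to Periods 3 and 4, can show only onsets after each participant's own end of treatment. A reader could mistake that figure for the typical time to onset.

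**Working it through.** The plan states no figure to reproduce. The check is to trace every planned output that could carry an on-treatment pituitary event.

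**Step 1: what section 5.5 specifies.** There are eight summaries: all events; serious events; onset from first dose (all, serious); onset from last prior dose (all, serious); duration (all, serious).

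| Period | Timing | Events of interest | Pituitary dysfunction |
|---|---|---|---|
| 1 | On treatment, to day 90 | 8 summaries | none |
| 2 | On treatment, after day 90 | 8 summaries | none |
| 3 | After treatment, to end of safety follow-up | 8 summaries | 8 summaries |
| 4 | After safety follow-up | 8 summaries | 8 summaries |

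These cells show where the restriction falls. They do not measure lost information. I assume events are assigned to a period by start date, which section 5.5 does not state.

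**Step 2: other routes for an on-treatment event.**
- SAP 5.4.4.2 (grouped incidence, onset, duration): not applicable, because pituitary dysfunction is not listed.
- SAP 5.4.4.1 and Table 3: the event is counted by preferred term, in system organ class tables, by worst grade (all treatment-emergent events), in the serious, grade 3 or higher, fatal, dose-interruption and discontinuation tables, and in the overall totals.
- TEAE listing: the event appears for the individual participant.
- Protocol 9.4.2.3.1: tables by system organ class and preferred term, with no pituitary group.

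None of these is a pituitary-specific participant count, and none summarizes pituitary onset or duration.

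**Step 3: can the count be recovered from single-term tables?** If the list has k terms with participant counts n₁ to n_k, the number N with at least one satisfies

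max(nᵢ) ≤ N ≤ n₁ + … + n_k,

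because one participant can have several terms. The documents give neither k nor any pituitary count, so these are assumptions:
- k = 1: N is known exactly.
- k equal counts: the upper limit is k times the lower, so 2-fold for two terms and 3-fold for three.
- Counts of 6, 4 and 3: lower limit 6, upper limit 6 + 4 + 3 = 13, ratio 13/6 = 2.2.

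The listing would resolve N by hand without new data.

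**Step 4: the onset summary.** For any event in Period 3 or 4, time from first dose is at least that participant's time on treatment. Protocol 4.1 expects a median treatment period of about 4 to 6 months. Onsets during treatment are excluded by construction.

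**Step 5: collection.** In this trial, protocol 8.4.6.1.1 collects all adverse events from first dose to the safety follow-up visit or 60 days after last dose, whichever is later. After that, 8.4.6.1.3 requires only serious events suspected to be related to investigational product. Periods 1 and 2 therefore have full collection and no grouped pituitary output, while Period 4 has restricted collection and the full set.

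**Step 6: would separate Period 1 and Period 2 columns be enough?** Not for the participant count. With P₁ and P₂ participants affected in each period, the on-treatment total lies between max(P₁, P₂) and P₁ + P₂. A combined count is also needed.

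**The case against.** The strongest reply is that nothing here is wrong. Section 5.5 exists to meet an FDA requirement that is not supplied and may itself set the pituitary scope at the post-treatment periods. The SAP objectives are open-ended, and data derivation is deferred to individual study SAPs that are also not supplied, so a grouped on-treatment table may exist elsewhere. The tiering is defensible too: protocol 2.3 classes cytokine release syndrome, ICANS and neutropenia as adverse drug reactions and pituitary dysfunction only as a possible concern. Tumor lysis syndrome has the same status and its own rule in Table 6-2, yet gets no grouped output in this SAP.

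Most of this stands. It sets the weight of the point and limits it to what this SAP specifies. It does not argue against using a term list already planned for the periods when dosing is managed, and the post-treatment output can stay as it is.

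A reader might infer that on-treatment pituitary events go uncollected or unreported. The documents do not support that: the events are collected from first dose in this trial and enter the general tables, totals and listing. A reader might also infer that the FDA requirement is not met. That cannot be judged without its text.

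**Conclusion.** The point holds as a minor gap in description. This SAP specifies no pituitary-specific grouped participant count, onset or duration summary for on-treatment events, and its only planned pituitary time-to-onset summaries cover post-treatment onsets. It would be too strong to call this an error or to say that a result is invalidated: SAP 5.2 plans no hypothesis testing, and no estimate changes.

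The practical size cannot be stated. It depends on how many terms the list contains, how often they occur and how far they overlap within participants, none of which the documents give. With a single term the count would not be ambiguous at all, although onset and duration would still go unsummarized. The conclusion assumes assignment of events by start date and does not extend to the unseen study SAPs.

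**What to change.** In SAP 5.5, replace the restriction of the pituitary summaries to Periods 3 and 4 with: *by Periods 1 to 4 and for the on-treatment period overall (Periods 1 and 2 combined, each participant counted once)*. Use the same Global Safety Officer term list and keep the Period 3 and 4 output for the postmarketing requirement. The event-of-interest list need not change.

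The cost is one phrase and three added columns (Period 1, Period 2, combined) across eight summaries, so 8 × 3 = 24 column entries in tables already planned. No new data collection and no new term list are needed.

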### 6. REFERENCES

Literature citations and references are detailed in the individual SAPs.

## 7. APPENDICES [AS APPROPRIATE]

### Appendix A. Handling of Incomplete Dates and Missing Dates for Adverse Events and Death

Below imputation rules will be used to impute start date and stop date of adverse events.

**Table 4. Imputation Rules for Partial or Missing Start Dates**

Start Date		Stop Date						missing	
		Complete: yyyymmdd		Partial: yyyymm		Partial: yyyy			
		< 1 st dose	≥ 1 st dose	< 1 st dose yyyymm	≥ 1 st dose yyyymm	< 1 st dose yyyy	≥ 1 st dose yyyy		
Partial: yyyymm	= 1 st dose yyyymm	2	1	2	1	n/a	1	1	
	≠ 1 st dose yyyymm		2		2	2	2	2	
Partial: yyyy	= 1 st dose yyyy	3	1	3	1	n/a	1	1	
	≠ 1 st dose yyyy		3		3	3	3	3	
Missing		4	1	4	1	4	1	1	

1 = Impute the date of first dose

2 = Impute the first of the month

3 = Impute January 1 of the year

4 = Impute January 1 of the stop year

Note: For participants who were never treated (first dose date is missing), partial start dates will be set to the first day of the partial month.

Note: If the start date imputation leads to a start date that is after the stop date, then do not impute the start date.

Imputation rules for partial or missing stop dates:

- For partial stop date mm-yyyy, impute the last of the month.
- For partial stop date yyyy, impute December 31 of the year.
- For completely missing stop date, do not impute.
- If the stop date imputation leads to a stop date that is after the death date, then impute the stop date as the death date.

- If the stop date imputation leads to a stop date that is before the start date, then there is a data error and do not impute the stop date. (ie. set the stop date as missing).

Imputation rules for partial or missing death dates:

- If death year and month are available but day is missing:
  - If mmYYYY for last contact date = mmYYYY for death date, set death date to the day after the last contact date.
  - If mmYYYY for last contact date < mmYYYY for death date, set death date to the first day of the death month.
  - If mmYYYY for last contact date > mmYYYY for death date, data error and do not impute.
- If both month and day are missing for death date or a death date is totally missing, do not impute.

Note that the last contact date refers to the last contact (i.e. a visit or an assessment) with participant instead of family members. Last contact date would be derived from the latest participant visit/assessment date.

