### Time to First Onset of Event of Interest (EOI) from First Tarlatamab Administration

Time to first onset of EOI will be derived as the number of days from first tarlatamab administration to start date of EOI.

Time to first onset of EOI from first tarlatamab administration (days) = (date of EOI - date of first tarlatamab administration) + 1

Time to first onset of EOI from first tarlatamab administration (hours) = datetime of EOI - datetime of first tarlatamab administration

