**5.4 Analysis Methods****5.4.1 General Considerations**

Descriptive statistics will be provided for exposure and safety endpoints. Descriptive statistics on continuous data will include means, medians, standard deviations, Q1, Q3, minimum, and maximum; while categorical data will be summarized using frequency counts and percentages. For time to safety event variables, Kaplan-Meier (KM) estimates and corresponding two-sided 95% confidence interval will be provided.

Data derivation from each study will follow their own principles specified in the individual study SAPs.

Imputation for missing or incomplete data may be performed if required. Incomplete adverse event and death dates will be imputed as described in Appendix A.

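### The SAP sets some unknown adverse event onsets to the first-dose date, and nothing keeps that date out of the days-to-onset, by-dose, duration and period tables

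*SAP*

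**What the plan says.** The SAP is an integrated plan for pooled safety data. Its Section 5.4.1 gives the general rule: "Incomplete adverse event and death dates will be imputed as described in Appendix A". Table 4 in Appendix A then assigns a code to each pattern of incomplete start date. The code at issue is "1 = Impute the date of first dose". It applies when the stop date is on or after first dose, or is missing, and the start is one of:

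- wholly missing;
- known only to the year, and that year is the first-dose year;
- known only to the month, and that month is the first-dose month.

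Two other codes cover a known month or year that differs from that of first dose: "2 = Impute the first of the month" and "3 = Impute January 1 of the year". The only written check on an imputed start is: "If the start date imputation leads to a start date that is after the stop date, then do not impute the start date".

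The start date is then used as follows:

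- Section 3, days to onset: "Time to first onset of EOI will be derived as the number of days from first tarlatamab administration to start date of EOI". A parallel definition counts days from the last prior dose.
- Section 3, duration of a resolved event: end date minus start date, plus 1.
- Section 5.4.4.2: "Summaries of treatment-emergent CRS (AMQ Narrow) by dose", among other by-dose displays.
- Section 5.5: events of interest by four periods. Period 1 runs to 90 days after cycle 1 day 1, or to end of treatment if earlier. Pituitary dysfunction is tabulated for Periods 3 and 4 only.

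None of these places exempts, flags or counts imputed starts, and no sensitivity analysis is planned for them.

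**The concern.** Setting an unknown onset to the first-dose date errs on the safe side when the question is whether an event counts as treatment-emergent. For questions of timing it is not conservative. It asserts the earliest possible on-treatment onset, so for any event that truly began after the first-dose day the error runs in one direction: earlier onset, earlier dose, earlier period, longer duration.

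Section 5.5 exists to meet a postmarketing requirement to characterise known serious risks by period. Late counts are likely to be small there, so single records matter. A pituitary event that began after end of treatment, with a year-only start in the first-dose year or no start date, would be placed in Period 1. It would then drop out of the only two period tables planned for that event type. The by-dose CRS displays separate cycle 1 day 1 from day 8, and a month-only date is enough to move an event between those two doses.

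**Working it through.** The SAP plans no hypothesis test (Section 5.2) and gives no figure to reproduce. The check applies Table 4 to dates.

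**Inputs.** Codes from Table 4. Onset day = event date − first-dose date + 1, and duration = end − start + 1, both from SAP Section 3. Doses on days 1, 8, 15, 29 and every 14 days after, from the Protocol regimen (Section 4.1). Period 1 ends 90 days after day 1 (SAP Section 5.5), with the participant still on treatment.

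**Step 1: the written check cannot help.** The first-dose code is used only when the stop date is on or after first dose, or missing. The imputed start therefore never falls after a known stop, so the start-after-stop note does not trigger for these records.

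**Step 2: worked dates, first dose 5 March.**

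- True onset 14 March, start recorded as that month only. True onset day is 14 − 5 + 1 = 10. The last prior dose is C1D8 on 12 March, so onset is 14 − 12 + 1 = day 3 from that dose. After imputation it is day 1 from C1D1.
- True onset 10 October, start recorded as that year only. There are 219 days from 5 March to 10 October, so the true day is 220. After imputation it is day 1, Period 1.
- The same October event lasting 10 to 13 October: true duration 4 days. With the imputed start, 5 March to 13 October is 222 + 1 = 223 days.

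**Step 3: all dates.** Table 4 was applied to every first-dose date in a 365-day year and every true onset from day 1 to 365, with the stop date missing or on/after first dose:

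| Known part of start | Code | Set to day 1 | Largest shift (days) | Last prior dose wrong | Period wrong |
|---|---|---|---|---|---|
| Nothing | 1 | always | 364 (limit of the range tested) | 98% | 75% |
| Year = first-dose year | 1 | always | 364 | 96% | 56% |
| Month = first-dose month | 1 | always | 30 | 60% | 0% |
| A different month | 2 | never | 30 | 75% | 4% |
| A different year | 3 | never | 363 | 96% | 37% |

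The percentages give every true onset day equal weight. They show which patterns are vulnerable and are not expected frequencies.

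**Step 4: effect on a summary, by assumption.** The documents give no count of incomplete dates and no onset distribution. Assume exponential onset with mean 60 days, and let a given share of events receive code 1:

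| Share given code 1 | Median onset (days) | Share on day 1 | Share later than 90 days after first dose |
|---|---|---|---|
| 0% | 42 | 1.7% | 21.9% |
| 1% | 41 | 2.7% | 21.7% |
| 2% | 41 | 3.6% | 21.4% |
| 5% | 39 | 6.6% | 20.8% |
| 10% | 36 | 11.6% | 19.7% |

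Medians move little. The visible change is the spike on day 1.

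**The case against.** The strongest reply is that few records will trigger the rule. In study 20210004 the onset date is a mandatory adverse event attribute (Protocol Section 11.4), participants return on C1D2 and C1D9, and data issues are to be resolved before lock as far as possible. CRS with an unknown month is hard to picture. This stands as a limit on size. It is weaker for events learned of in long-term follow-up, which may be by telephone or chart review (Protocol Section 8.1.5). Protocols for the other two pooled studies are not available.

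The second reply is that no sentence in the SAP says imputed starts enter the timing tables. Section 5.4.1 also states: "Data derivation from each study will follow their own principles specified in the individual study SAPs". Those study SAPs are not supplied and could restrict the use. This stands too: the link follows from a general rule with no exemption, not from an explicit instruction. If a study SAP already restricts it, a cross-reference would be enough.

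A reader might go further and infer three things that the documents do not support:

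- That late events in general are moved to day 1. Codes 2 and 3 keep starts with a known later month or year off day 1, although they too can bring the onset forward.
- That the hours-based CRS onset tables are distorted. They need a date and time, and Appendix A imputes no clock times.
- That the share of late events lost equals the share of incomplete dates. A late event missing only its day receives code 2 and normally keeps its period.

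**Conclusion.** The point holds in a limited form. Followed as written, the SAP places three kinds of incomplete start on day 1 after the first dose, which is the step dose in the 1 to 10 mg regimen but not necessarily in every pooled cohort. Wholly missing starts, and year-only starts in the first-dose year, can also leave Periods 2 to 4 for Period 1 and can inflate durations greatly. Month-only starts in the first-dose month shift by at most 30 days. Their dose can change, but their period normally cannot unless treatment ended within that month.

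This rests on two assumptions: that the true onset was after the first-dose day, and that no study SAP limits the use of imputed dates. The number of affected records is unknown and may be small, and the analyses are descriptive. Even so, the rule gives systematically early timing where onset is least known, and it is easy to correct before the tables are produced.

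**What to change.** State in Appendix A that imputed start dates serve only to set treatment-emergent status. Where the imputed part would decide the onset day, last prior dose, duration or period:

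- keep the event in the incidence counts;
- show it in an 'onset unknown' row of the timing, by-dose, duration and period displays;
- report how many events fall in that row.

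The row is better than dropping the events, because dropping them would itself hide possible late events. In study 20210004 a separate field records whether the event began before first dose (Protocol Section 11.4), so treatment-emergent status need not rest on the imputed date alone.

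Optionally, add one sensitivity run using the latest start consistent with the known part of the date, bounded by the earliest of stop date, death, end of study or data cutoff.

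The cost is a sentence in Appendix A, one extra row per display, and slightly fewer events with an assigned time.

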**Duration of Adverse Event**

$$\text{Duration of resolved adverse events (days)} = (\text{event end date} - \text{event start date}) + 1$$

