### Time to Adverse Event Resolution

Time to resolution is defined as the interval from the event start date to event end date. Unresolved events are censored at last dose of tarlatamab date + 65 days, end of study date, death date or analysis cutoff date, whichever occurs earlier.

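### Imputed adverse event stop dates have no limit at the analysis cutoff, so a resolved event can be given an end date later than the data and an overstated duration

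*SAP*

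**What the plan says.** Section 5.4.1 of the integrated SAP refers incomplete adverse event dates to Appendix A. After Table 4, Appendix A gives these rules for stop dates:

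- Year only: "For partial stop date yyyy, impute December 31 of the year".
- Month and year: "For partial stop date mm-yyyy, impute the last of the month".
- Nothing recorded: "For completely missing stop date, do not impute".
- Upper check: if the imputation "leads to a stop date that is after the death date, then impute the stop date as the death date".
- Lower check: "If the stop date imputation leads to a stop date that is before the start date, then there is a data error", and the stop date is set to missing.

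No rule mentions the analysis cutoff, end of study or last contact as a limit on a stop date.

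Section 3 defines duration for resolved events as end date minus start date plus 1. It also defines time to resolution, and there the cutoff does appear: "Unresolved events are censored at last dose of tarlatamab date + 65 days, end of study date, death date or analysis cutoff date", whichever comes first. That limit is written for unresolved events only.

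Durations are summarised in Section 5.4.4.2 for events of interest, including subsets by grade and participants with CRS who required tocilizumab, and in Section 5.5 by postmarketing period. Section 5.4.1 specifies mean, median, SD, quartiles, minimum and maximum for continuous data.

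**The concern.** A cutoff defines what can have been observed. When a stop date is known only to lie in the cutoff year and the cutoff comes before 31 December, the rule gives the event an end date on which no data exist. The duration formula then takes that date at face value.

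The tables exposed are those on duration of CRS, ICANS, neutropenia, neurological and hypersensitivity events. They support a filing (Section 1) and an FDA postmarketing requirement (Section 5.5). One extreme record can set the maximum and shift the mean and SD, most visibly in small subsets such as higher-grade events or tocilizumab-treated CRS.

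**Working it through.** The plan gives no figure to reproduce here. The check is calendar arithmetic on its own definitions.

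**Inputs.** The imputed stop is 31 December of the stop year, or the last day of the stop month (Appendix A). Duration = end − start + 1 (Section 3). The documents do not state the cutoff date, so it is assumed and varied over a 365-day year.

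**Step 1: days past the cutoff, year-only rule, stop year = cutoff year.** Excess = 31 December − cutoff.

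| Assumed cutoff | Excess (days) |
|---|---|
| 31 January | 334 |
| 31 March | 275 |
| 30 June | 184 |
| 30 September | 92 |
| 30 November | 31 |
| 31 December | 0 |

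**Step 2: month-year rule.** The worst case is a cutoff on the first of a 31-day month: 31 − 1 = 30 days.

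**Step 3: one event (assumed dates).** A 4-day event runs from 10 to 13 January, with only the year of the stop recorded.
- True duration: 13 − 10 + 1 = 4 days.
- Current rule: 10 January to 31 December = 355 + 1 = 356 days, overstated by 352.
- Capped at a 30 June cutoff: 171 + 1 = 172 days, still overstated by 168.
- Capped at 31 January, 31 March or 30 September: 22, 81 or 264 days.

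**Step 4: how much a cap removes on average.** Take an event starting 15 January, a 30 June cutoff, and a true end uniform between them.
- Current rule: mean overstatement (350 + 184)/2 = 267 days.
- With the cap: (166 + 0)/2 = 83 days.
- The difference, 184 days, is the excess in Step 1. The cap removes only the part after the cutoff.

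**Step 5: earlier years.** If the stop year precedes the cutoff year, 31 December is before the cutoff and a cutoff cap changes nothing. Overstatement in a living participant can still be 0 to 364 days (365 in a leap year).

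**Step 6: effect on a summary (hypothetical counts).** Take 100 events, all of 4 days, one of them recorded as in Step 3.
- Current rule: mean (99 × 4 + 356)/100 = 7.52 days, maximum 356.
- Capped at 30 June: mean (99 × 4 + 172)/100 = 5.68 days, maximum 172.
- Median: 4 days either way.

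The documents do not say how many stop dates are year-only, so Step 6 illustrates sensitivity and is not a forecast.

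**The case against.** The strongest objection is that the rule will seldom matter. A post-cutoff date needs a year-only stop date, a stop year equal to the cutoff year, a cutoff before 31 December and no earlier death date, all together. (The month-year rule needs the same coincidence within a month.) The protocol makes onset and resolution dates mandatory event attributes (Section 11.4) and plans completeness checks before each lock (Section 9.4.1). CRS is recorded in particular detail, with a new record for each rise in grade (Section 11.11.1). The protocol cites a median survival of 10 months after progression, so the death limit may often bind. Output is descriptive (Section 5.2 of the integrated SAP), and longer durations do not flatter the drug. All of this stands and keeps the point minor. The death limit is not a complete safeguard, because a death date lacking both month and day is not imputed.

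A second objection is that the individual study SAPs, which Section 5.4.1 says govern data derivation, may hold a cap. They were not available here. The same section sends incomplete adverse event dates specifically to Appendix A, which has none.

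Two stronger readings are tempting and should be resisted.

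- A reader might infer that events are wrongly counted as resolved. They are not: a recorded stop year says that the event ended. Only the day, and so the duration, is wrong.
- A reader might infer that ended events are ranked above ongoing ones in the duration tables. Section 3 restricts duration to resolved events, so ongoing events do not enter them. The contrast exists only for time to resolution, and Sections 5.4.4 and 5.5 name no summary of that quantity.

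**Conclusion.** Wrong as written, but minor. Appendix A permits a stop date later than the analysis cutoff: by up to 334, 184 or 92 days for assumed cutoffs of 31 January, 30 June or 30 September under the year-only rule, and by at most 30 days under the month-year rule. This requires a stop year (or month) equal to that of the cutoff and no earlier death date. The consequence is an impossible end date and an overstated duration, felt in means, SDs and maxima.

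A reader might conclude that CRS durations will be materially inflated, or that a cutoff cap would cure the overstatement. The documents support neither. The count of partial dates is unknown, and much of the overstatement comes from choosing 31 December at all. In the worked example a 4-day event still shows 172 days after a 30 June cap.

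**What to change.** Add one sentence to Appendix A: an imputed stop date may not be later than the earliest of the death date, the end of study date and the analysis cutoff date. Section 3 already uses all three, so this costs one sentence and one line of code.

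Because the cap does not correct overstatement before the cutoff or in earlier years, also footnote the number of year-only stop dates in each duration table and show the duration summaries with and without those records. That means one rerun of existing tables.

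Do not censor these events as unresolved. They are known to have ended, and the duration summary is defined for resolved events.
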